#### 1.4.2.3 Ongoing Studies

Data from an ongoing open-label extension study (Study FGCL-4592-059, to which some subjects from Studies FGCL-4592-041 and FGCL-4592-040 rolled over) further shows durability of roxadustat effect in maintaining Hb levels in subjects with CKD over 52 to 76-week treatment as of 07 September 2013.

#### 1.4.3 Safety

The overall frequency and type of treatment-emergent adverse events (TEAEs) and treatment-emergent serious adverse events (TESAEs) observed in these clinical studies reflect events that would be expected to occur in CKD subjects with multiple co-morbidities and on a number of concomitant medications. Safety analyses did not reveal any association between the rates of occurrence of cardiovascular events with roxadustat, or any effect on adverse event (AE) rates related to either increasing Hb levels or on the rate of change of Hb levels.

As of 7 September 2013, a total of 969 subjects have been exposed to roxadustat in the clinical development program, comprising 377 healthy subjects, 294 NDD-CKD subjects, and 298 DD-CKD subjects. In the healthy subject trials, most subjects were male as enrollment in these trials was generally restricted to men. In the NDD-CKD and DD-CKD studies roughly half of the subjects were male. Most of the healthy subjects were Asian or Caucasian, reflecting the countries where these studies were conducted (Europe, United Kingdom, US, China, and Japan). Most NDD-CKD and DD-CKD subjects were either Caucasian or African-American, as most trials for which demographic data are pooled were conducted in the United States or Eastern Europe. In general, the most commonly reported AEs ( $\geq 4\%$  and  $\geq 1\%$  above placebo rate) in healthy volunteers were headache and dizziness. The most commonly reported AEs ( $\geq 5\%$ ) in subjects with NDD-CKD were diarrhea, nausea, urinary tract infection, nasopharyngitis, peripheral edema, hyperkalemia, headache, and hypertension (none were  $\geq 8\%$ ). The most commonly reported AEs ( $\geq 3\%$ ) in subjects with DD-CKD were diarrhea, nausea, hypertension, and upper respiratory tract infection (none were  $\geq 5\%$ ). Adverse event rates of hypertension (1% in Study FGCL-SM4592-017 and 7.6% in Study FGCL-4592-041) and thrombosis (overall incidence  $< 1\%$ ), compare favorably with the rates reported in published ESA studies in similar patient populations (Krapf, 2009). No safety risks were associated with rate of rise of Hb levels or with achieving an Hb level above 11 g/dL using roxadustat. Study FGCL-4592-041 subjects achieved Hb  $> 11$  g/dL in  $> 50\%$  of exposure time during study, and there were no

Liver parameters were monitored closely throughout the roxadustat clinical development program. Increases in liver parameters were infrequently seen, and were generally mild and transient in nature. No cases of Hy's Law were observed throughout the program. An independent data and safety monitoring committee concluded that there was no concern for hepatotoxicity with roxadustat. Based on the safety data collected to date, roxadustat is generally well tolerated and has an acceptable safety profile that supports its further development.

In summary, the cumulative safety data have not identified major risks related to roxadustat. At therapeutic doses, roxadustat is well tolerated by healthy subjects and subjects with CKD. Potential additional benefits of roxadustat compared with ESAs for the treatment of NDD-CKD and DD-CKD anemia include efficacy without the need for IV iron supplementation, and a favorable change in lipid profile.

Taking into account the general measures taken to minimize risk to subjects participating in the Phase 3 clinical trials, the anticipated benefits of treating the anemia associated with CKD in subjects on dialysis and not on dialysis, the data support conduct of Phase 3 trials. For detailed safety information, please refer to the most current version of the IB.

## 1.5 Summary

In summary, roxadustat is an orally active HIF-PHI with erythropoietic effects. Intermittent dosing of roxadustat results in transient activation of HIF, intermittent induction of endogenous

physiologic-range EPO, and dose-dependent erythropoiesis, suggesting a coordinated mechanism of erythropoiesis that is different from ESA therapy, including beneficial effects on iron handling. The clinical data collected thus far suggest that roxadustat is generally safe and well tolerated in healthy adult subjects, and in dialysis and nondialysis CKD subjects with anemia treated up to 60 weeks.

## 1.6 Roxadustat Dose Rationale

Starting doses of roxadustat were studied in three ways in the Phase 2 program: using a strict weight-based dosing approach that was useful in the proof of concept stage; using a tiered weight-based approach where a subject's starting dose was selected based on categorizing the subject's body weight as low (45 to < 70 kg), medium (70 to 100 kg), or heavy (> 100 kg); and using an absolute starting dose regardless of body weight. The tiered weight-based approach has been chosen for the development of roxadustat in the Phase 3 program to provide a practical starting dose strategy for a controlled Correction to target Hb values, based on the observed relationship between body weight, PK, and Hb response, and the requirements of oral dosing.

The tiered, weight-based starting doses selected for this study consist of the following roxadustat doses: 70, and 100 mg, for low weight ( $\leq 70$  kg), and high weight ( $> 70$  to 160 kg) subjects, respectively. These dose tiers are based primarily on the interim safety and efficacy data generated in the CKD nondialysis Correction of anemia study (FGCL-4592-041) and confirmed by the dialysis study. These doses will be administered at a frequency of TIW. Using this dosing scheme, subjects will receive starting roxadustat doses between 0.9 mg/kg TIW for the heaviest subject, and 1.6 mg/kg TIW for the lightest subject. This is comparable to the starting doses of 1.0 to 1.6 mg/kg, which were the doses that effectively corrected Hb levels in studies FGCL-4592-041 and FGCL-4592-053. Further dose adjustment to achieve Correction and subsequent Maintenance is based upon regular monitoring of Hb.

Based on the Phase 2 data, it is expected that subjects who receive these starting doses to correct anemia will be able to maintain Hb levels with a total weekly dose reduction of the order of 22 to 35%. This dose reduction can be achieved by adjusting the per dose amount towards the protocol-defined Hb target range. The Phase 2 studies evaluated the need for dose adjustments for both Hb Correction and Hb Maintenance. Dose adjustments were allowed at regular 4-week intervals to maintain, increase, or decrease the dose according to prespecified rules. Pre-specified dosing steps were used to correct and maintain Hb levels within treatment thresholds based on absolute Hb levels and change of Hb in the previous 4 weeks. Additional rules for dose adjustment were provided to minimize excessive hematopoiesis. These dose adjustment rules were successful in Hb Correction and Hb Maintenance and will be adopted in this study with minor modifications.

## 1.7 Risks/Benefits of Roxadustat Treatment

The primary benefit of roxadustat is the treatment of anemia, including the relief of associated signs and symptoms and an increased quality of life. Roxadustat is expected to be at least as safe as ESAs, and the current data suggest that cardiovascular risk may be lower than with ESAs.

An established dose adjustment algorithm will be used during the study to titrate roxadustat doses to enable subjects to achieve and maintain optimal Hb levels, while closely monitoring the rate of rise of Hb levels. Roxadustat doses may be held and/or the use of therapeutic phlebotomy is allowed in the event of excessive hematopoiesis. Adverse and serious adverse events (SAEs),

and laboratory parameters including electrolytes, liver enzymes, and iron indices, will be closely monitored to ensure the safety of treatment with roxadustat and epoetin alfa. An independent expert panel will assess and adjudicate prespecified cardiovascular, cerebrovascular and thromboembolic events. In addition, an independent Data and Safety Monitoring Board (DSMB) will perform regular, periodic assessments of safety data to detect any potential safety signals that may arise during the study and advise the Sponsor accordingly.

Based on the clinical and nonclinical trial results to date, it is anticipated that orally administered roxadustat will be comparable in efficacy to marketed parenteral ESA products in the treatment of anemia of CKD, with an acceptable safety profile. Roxadustat may offer a valuable alternative to the current treatment options in the management of anemia of CKD.

## 2 OBJECTIVES

### 2.1 Primary Objectives

Evaluate the Efficacy and Safety of Roxadustat in the Treatment of Anemia in Incident-Dialysis Subjects, Compared with Active Control.

### 2.2 Secondary Objectives

The secondary objectives in this study are to:

- Evaluate the utilization of IV iron with roxadustat compared with Active Control
- Evaluate the effect of roxadustat on serum lipid parameters compared with Active Control
- Evaluate the effect of roxadustat on BP compared with Active Control
- Evaluate time to achieve a Hb response compared with Active Control

## 3 STUDY DESIGN

### 3.1 Description of the Study

This is a Phase 3, multicenter, randomized, open-label, and active-controlled study to evaluate the efficacy and safety of roxadustat in the treatment of anemia in incident-dialysis subjects.

The study periods are as follows:

- **Screening Period:** Up to 6 weeks
- **Treatment Period:** Treatment duration is variable for individual subjects. In order to complete the Treatment Period simultaneously for all study subjects, the minimum treatment duration may be less than 52 weeks, with a maximum treatment duration of up to approximately 3 years after the last subject is randomized. Subjects will be informed at least 4 weeks prior to their treatment period end.
- **Post-Treatment Follow-Up Period:** 4 weeks

### 3.2 Randomization and Treatment Assignment

A total of up to approximately 1200 subjects will be randomized in a 1:1 ratio to receive either open-label roxadustat or epoetin alfa ([Appendix 1](#)).

Randomization is stratified by the following factors:

- Geographical region
- Screening Hb values ( $\leq 8$  g/dL vs.  $> 8$  g/dL)
- Cardiovascular/cerebrovascular/thromboembolic medical history (Yes vs. No)

Randomization schedules will be prospectively prepared. Automated randomization and treatment assignments will be provided by an Interactive Voice and Web Response System (IXRS).

### 3.3 Procedures for Handling Incorrectly Enrolled Subjects

Subjects who fail to meet all eligibility criteria should not be enrolled.

If it is discovered in retrospect that a subject did not meet all eligibility criteria, the Investigator should inform the Medical Monitor immediately, and a discussion should occur regarding whether or not to discontinue the study subject. All decisions from such a discussion should be appropriately documented.

### 3.4 Replacement of Subjects

Subjects who drop out prematurely will not be replaced in the study.

### 3.5 Study Treatment

#### 3.5.1 Dose and Schedule

Eligible subjects will be randomized via IXRS to receive either roxadustat or epoetin alfa. The first study drug administration will be on Day 1 (Week 0).

### 3.5.2 Starting Dose of Study Drug

#### 3.5.2.1 Roxadustat Arm

For subjects receiving roxadustat, the initial dose (per dose amount) is based on a tiered, weight-based dosing scheme ([Table 1](#)). Roxadustat will be dosed orally TIW throughout the Treatment Period, except if a subject requires < 20 mg TIW (ie, < 60 mg per week) to maintain Hb levels in the Maintenance Phase, the dosing frequency should be reduced in a step-wise fashion eg, TIW to BIW, BIW to QW, QW to Q-2 Week etc.

#### 3.5.2.2 Active Control Arm (Epoetin alfa)

Subjects on HD will initiate intravenous (IV) treatment according to the epoetin alfa US Package Insert (USPI) or Summary of Product Characteristics (SmPC).

For subjects on HHD or PD, epoetin alfa will be administered according to the epoetin USPI, or SmPC or local standard-of-care.

For countries using prefilled syringes, the initial epoetin alfa dose and dose adjustments should be approximated to the closest weekly dose.

**Table 1** Initial Study Drug Dosing

Study Drug (Dose Frequency)	Low Weight (≤ 70 kg)	High Weight (> 70 to 160 kg)
Roxadustat (TIW)	70 mg	100 mg
Active Control HD (TIW)	IV dosing according to epoetin alfa Package Insert or SmPC.	
Active Control PD/HHD	Epoetin alfa should be administered according to the epoetin alfa Package Insert or SmPC or local standard of care.	

Abbreviations: HD = hemodialysis; HHD= home-hemodialysis; PD = peritoneal dialysis; SmPC = summary of product characteristics; TIW = three times a week.

Note: Weight in HD subjects = subject's dry weight.

### 3.5.3 Dose Adjustment for Roxadustat

Dose adjustments will occur in two separate study dosing phases: the Correction Phase and the Maintenance Phase. Each of these phases will follow unique adjustment rules according to [Appendix 2](#).

All subjects will be dosed orally TIW during the Treatment period. The maximum roxadustat dose is 3.0 mg/kg per dose or 400 mg (whichever is lower).

All dose adjustments as well as assessments of excessive hematopoiesis are based on Hb values using a point-of-care device, such as HemoCue® or CritLine®. In the event that the central lab Hb value of the site visit is significantly different and the dose adjustment decision based on the HemoCue® / CritLine® value is being re-considered, the Medical Monitor should be contacted, if possible.

The determination of Hb response and transition from the Correction to the Maintenance Phase of the study is based on the central laboratory Hb value.

### 3.5.3.1 Correction Phase of Dosing for Roxadustat

- The aim of the Correction Phase is to increase Hb levels from baseline to the target Hb level by using the dose adjustment algorithm in [Appendix 2](#).
- This phase is variable in length for each subject.
- Dose adjustment reviews will occur on Week 4, and at intervals of every 4 weeks thereafter (Weeks 8, 12, 16, etc.), except in the event of excessive hematopoiesis, in which case doses may be adjusted at any time. In such cases, dose adjustment reviews are resumed at 4-week intervals. For example, if the subject's Hb increases  $> 2.0$  g/dL from Week 1 to Week 3, the subject's dose is reduced by one dose step at Week 3. The next dose adjustment review should occur 4 weeks later at Week 7 and at 4-week intervals thereafter.
- If the dose adjustment interval falls on a non-study visit week (starting Week 4), the dose adjustment review should be performed at the next scheduled study visit if a dose adjustment was not required at the previous visit. For example, if a subject's visit is scheduled for Weeks 6 and 8, and the dose adjustment would occur at Week 7, then the dose adjustment should be evaluated at the Week 8 visit.

### 3.5.3.2 Maintenance Phase of Dosing for Roxadustat

- The aim of the Maintenance Phase is to maintain Hb levels after the initial correction by using the dose adjustment algorithm in [Appendix 2](#).

Note: Given the complexity in roxadustat dose adjustments, and the need to take into account the various clinical parameters in roxadustat dose titration, one would not consider it a protocol deviation when study subjects are dosed based on their clinical circumstances, whether or not it is concordant with the roxadustat dose adjustment guidelines unless it was related to "excessive hematopoiesis" (eg, Hb  $\geq 13$  g/dL, requiring a dose hold) or "Overdose" (prescribed  $>3.0$  mg/kg per dose or 400 mg per dose whichever is lower).

### 3.5.3.3 Active Control (Epoetin alfa) Subjects

Epoetin alfa subjects should maintain their Hb levels within the target range accepted by health authorities, specifically:

- Hb 10 to 11 g/dL in the United States (US)
- Hb 10 to 12 g/dL in countries outside the US

Hemodialysis subjects will be dosed IV TIW, with starting doses and dose adjustment rules according to the epoetin alfa USPI or SmPC. In subjects requiring ultra-low dose of EPO (eg,  $\leq 1000$  IU/per week), frequency of administration may be adjusted per local standard of care.

Home-hemodialysis and peritoneal dialysis subjects will be dosed according to the epoetin Package Insert or the SmPC or local standard of care.

For countries using prefilled syringes, the initial epoetin alfa dose and dose adjustments should be approximated to the closest weekly dose.

Note: Given the complexity in EPO dose adjustments and the need to take into account the various clinical parameters in EPO dose titration, one would not consider it a protocol deviation

when study subjects are dosed according to local standard of care whether or not it is concordant with package insert/SmPC

ESA administration in roxadustat subjects during hospitalization is not considered a protocol deviation if roxadustat is not allowed or available during that hospitalization.

### 3.5.3.4 Excessive Hematopoiesis

For subjects randomized to Roxadustat, the following scenarios are defined as “excessive hematopoiesis”

- Hb increases by  $> 2.0$  g/dL at any time within a 4 week period: reduce the dose by one dose step.
- Hb reaches or exceeds 13 g/dL: hold dosing, check Hb weekly. Resume dosing when Hb  $< 12.0$  g/dL (for US subjects central lab Hb value preferred), at a dose that is reduced by two dose steps.

For subjects on prolonged dose-hold, with stable (not dropping) Hb, the Investigator may use discretion to schedule less frequent visits.

Anytime Hb is assessed via HemoCue®/CritLine®/local lab, a central lab Hb should be obtained as well.

## 3.6 Concomitant Medications, Procedures and Nondrug Therapies

### 3.6.1 Concomitant Medications

Concomitant medications are any prescription or over-the-counter preparations, including herbal products and “natural remedies”, used by a subject while participating in this clinical study.

For all concomitant medication use, an indication for its use should be provided. If the stated indication is a nonspecific condition (eg, “rash”) documentation of the condition, as specific as possible, should be maintained in the subject’s clinical study records as source documentation.

To avoid confounding effects on study endpoints, changes to anti-hypertensive medications should be minimized, and made only if deemed medically necessary by the Investigator or if prespecified changes BP are met.

#### 3.6.1.1 Use of Phosphate Binders During the Study (Roxadustat Subjects)

When coadministered with roxadustat, in a clinical pharmacology study, the bioavailability of roxadustat was reduced. Subjects should be advised to discuss with the Investigator when changing the dose or dosing time of their phosphate binder while taking roxadustat. To optimize the absorption of roxadustat, subjects should be advised that roxadustat be taken at least one hour before or three hours after their phosphate binder if possible.

#### 3.6.1.2 Use of Hydroxymethylglutaryl Coenzyme A (HMG-CoA) Reductase Inhibitors (Statins) During the Study (Roxadustat Subjects)

When coadministered with roxadustat, in clinical pharmacological studies, hydroxymethylglutaryl coenzyme A reductase inhibitor (statin) exposure was increased 2- to 3-fold. For patients randomized to roxadustat, investigators should consider this interaction and local prescribing information when deciding on the appropriate statin dose for individual patients, bearing in mind the impact of ethnicity, other concomitant medications, renal and hepatic function. Goals of lipid

lowering treatment should be maintained as clinically indicated. The dose of statins should not exceed the recommended daily dose in [Table 2](#) for subjects randomized to roxadustat.

**Table 2 Recommended Maximum Daily Dose of Statins for Subjects Randomized to Roxadustat**

Statin	Proposed Max Dose (mg/day)
Simvastatin	5
Atorvastatin	40
Rosuvastatin	5
Fluvastatin	40
Pitavastatin	2
Pravastatin	40
Pitavastatin	1
Lovastatin	20

Abbreviations: max = maximum.

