### 6.1.2.2 Weeks 1 to 4 (Weekly, $\pm 2$ days)

- Laboratory tests (must be performed prior to dosing):
  - Weeks 1, 2, 3, 4, CBC with WBC differential.
  - Week 2: LFTs only
  - Week 4: Serum chemistry
  - Week 4: Lipid panel (fasting whenever possible)
  - Week 4: Serum iron, ferritin, TIBC, TSAT.
  - Week 4: CHr
  - Weeks 1, 2: Reticulocyte count
  - Week 4: Special laboratory analytes
  - Week 4: Archival serum/plasma samples (optional donation, separate consent form)
- HemoCue®/CritLine® assessment.
- Dose adjustment review beginning Week 4 and at 4-weekly intervals thereafter (except in the event of excessive hematopoiesis). Refer to [Section 3.5.3](#), and [Appendix 2](#).
- All visit weeks: BP and HR
- Adverse event recording
- Concomitant medication recording
- Procedures and nondrug therapy recording
- Dispense study drug every 2 weeks (Week 2 and Week 4)

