### 6.1.2.3 Weeks 6 to 24 (Every 2 weeks, $\pm 4$ days)

- Laboratory tests (must be performed prior to dosing):
  - Weeks 8, 12, 20: CBC with WBC differential
  - Week 6 followed by every visit where no CBC is collected; Hb only.
  - Weeks 8, 12, 20: Serum chemistry
  - Weeks 6, 16: LFTs and CPK
  - Weeks 8, 12, 24: Lipid panel (fasting whenever possible).
  - Weeks 8, 12, 20: Serum iron, ferritin, TIBC, TSAT.
  - Weeks 8, 12, 20: CHr
  - Week 12: HbA1c
  - Weeks 8, 20: Reticulocyte count
  - Weeks 12, 20: Special laboratory analytes

- Weeks 12, 20: Archival serum/plasma samples (optional donation, separate consent form)
- HemoCue®/CritLine® assessment
- Weeks 12, 24: Serum hCG pregnancy test for women of childbearing potential (for definition, see [Section 3.6.6](#))
- 
- Week 24 followed by every 12 weeks: Targeted physical exam (eg, respiratory and cardiovascular system)
- Week 24 followed by every 24 weeks: 12-lead ECG, weight (HD subjects: dry weight)
- Dose adjustment review every 4 weeks (except in the event of excessive hematopoiesis or dose frequency conversion). Refer to [Section 3.5.2](#), and [Appendix 2](#).
- All visit weeks: BP and HR
- Week 12 HRQoL questionnaires (SF-36, FACT-An, and EQ-5D-5L)
- Adverse event recording
- Concomitant medication recording
- Procedures and nondrug therapy recording
- Dispense study drug

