#### 6.1.2.4 Weeks 28 to End of Therapy (Every 4 weeks, ±4 days)

- Laboratory tests (must be performed prior to dosing):
  - Week 28 followed by every 8 weeks: CBC with WBC differential
  - Week 32 followed by every visit where no CBC is collected; Hb only
  - Week 28 followed by every 8 weeks: Serum chemistry
  - Weeks 32, 40, 48, 60 followed by every 24 weeks: Lipid panel (fasting whenever possible)
  - Week 28 followed by every 8 weeks: Serum iron, ferritin, TIBC, TSAT
  - Week 28 followed by every 8 weeks: CHr
  - Weeks 28, 44, 60, followed by every 16 weeks: HbA1c
  - Week 44 followed by every 24 weeks: Reticulocyte count
  - Week 44, followed by every 24 weeks: Special laboratory analytes

- Week 44 followed by every 24 weeks: Archival serum/plasma samples (optional donation, separate consent form)
- All visit weeks: HemoCue®/CritLine® assessment.
- Week 36 followed by every 12 weeks: Targeted physical exam (eg, respiratory and cardiovascular system)
- Week 36, followed by every 12 weeks: Serum hCG test for women of childbearing potential (for definition, see [Section 3.6.6](#))
- All visit weeks: Dose adjustment review (except in the event of excessive hematopoiesis or dose frequency conversion). Refer to [Section 3.5.2](#), and [Appendix 2](#).
- All visit weeks: BP and HR
- Weeks 36 and 52: HRQoL questionnaires (SF-36, FACT-An, and EQ-5D-5L)
- Adverse event recording
- Concomitant medication recording
- Procedures and nondrug therapy recording
- Dispense study drug

\* If the indicated assessments fall on a study treatment visit that is within two weeks of the planned EOT visit, then these specified assessments can be postponed until the EOT visit.

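### Protocol Table 2 gives pitavastatin two different maximum daily doses, 2 and 1 mg/day, and nothing says which applies

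*Protocol*

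**What the plan says.** Protocol section 3.6.1.2 reports that roxadustat raised statin exposure 2- to 3-fold in clinical pharmacology studies. It leaves individual dosing to judgment: "investigators should consider this interaction and local prescribing information when deciding on the appropriate statin dose for individual patients". It then sets an upper limit for the roxadustat arm: "The dose of statins should not exceed the recommended daily dose in" Table 2.

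Table 2, "Recommended Maximum Daily Dose of Statins for Subjects Randomized to Roxadustat", has one dose column, headed "Proposed Max Dose (mg/day". Its rows, in order, are:

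| Row | Statin | Maximum (mg/day) |
|---|---|---|
| 1 | Simvastatin | 5 |
| 2 | Atorvastatin | 40 |
| 3 | Rosuvastatin | 5 |
| 4 | Fluvastatin | 40 |
| 5 | Pitavastatin | 2 |
| 6 | Pravastatin | 40 |
| 7 | Pitavastatin | 1 |
| 8 | Lovastatin | 20 |

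The only note under the table expands an abbreviation.

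**The concern.** A drug-interaction limit should give every site the same answer. For pitavastatin this table gives two answers that differ by a factor of two. With up to approximately 400 centers planned, one site could treat 2 mg/day as acceptable while another treats the same dose as over the limit, and each could point to a row in support.

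There is a second possibility. If one of the two rows was meant for a different statin, then that statin has no limit in the table at all. Only the sponsor can say whether row 5 or row 7 is a leftover value, a duplicate or a misnamed drug.

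**Working it through.** No power or error-rate calculation applies. The check is a reading of the table against the rule that invokes it.

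**Row count.** Six statins appear once and pitavastatin appears twice: 6 + 2 = 8 rows and 6 + 1 = 7 distinct statins. So 2 of 8 rows, covering 1 of 7 statins, conflict.

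**Where the two rows disagree.** For a pitavastatin dose d in mg/day:

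| Dose | Row 5 (maximum 2) | Row 7 (maximum 1) |
|---|---|---|
| d ≤ 1 | within | within |
| 1 < d ≤ 2 | within | over |
| d > 2 | over | over |

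The conflict is confined to doses above 1 and up to 2 mg/day.

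**Whether anything separates the rows.** Neither row carries a region, ethnicity, formulation or organ-function label. Section 3.6.1.2 names ethnicity, other medication, and renal and hepatic function as general considerations, but does not tie any of them to a row. No other section of the Protocol or SAP gives a statin dose limit. Section 8.4.6 on protocol deviations points to guidance for roxadustat, epoetin alfa and IV iron, not statins.

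**Whether the table could have been damaged in conversion.** It reads as eight complete name-and-dose pairs under a two-column header, so a conversion fault looks unlikely. The sponsor can check this against its own copy.

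**Safety monitoring already planned.** Table 3 places CPK and the liver tests in the chemistry panel. Counting scheduled on-treatment draws through Week 52 that include both:

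- Section 6.1.2: "Week 4: Serum chemistry"; "Weeks 8, 12, 20: Serum chemistry"; "Week 28 followed by every 8 weeks: Serum chemistry", which gives Weeks 28, 36, 44 and 52; and "Weeks 6, 16: LFTs and CPK". That is 1 + 3 + 4 + 2 = 10. The Week 2 draw is described there as liver tests only and is not counted.
- Appendix 3: chemistry at Weeks 2, 8, 12, 20, 28, 36, 44 and 52, plus liver tests and CPK at Weeks 6 and 16. That is 8 + 2 = 10.

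Screening, Day 1, end of treatment and end of study are additional. The two schedules differ on whether the early chemistry draw is at Week 2 or Week 4. That is a separate discrepancy and does not change the total.

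**The case against.** The duplicate is plain, so the case on the other side is about weight and remedy.

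- **The limit is soft.** The title calls the doses recommended, the column calls them proposed, and the investigator is asked to individualise. This is fair as a description of tone. But the text still tells sites not to go above the tabulated dose. Judgment can choose a dose below a limit; it cannot say which of two limits applies.
- **A cautious site can comply anyway.** A dose of 1 mg/day or less meets both rows. That is true, but no text tells sites to read the table that way.
- **Monitoring covers the risk.** Ten draws by Week 52 do reduce the practical risk. They detect a problem after exposure and do not define the permitted dose.
- **LDL is a secondary endpoint.** The change in LDL over Weeks 12 to 24 is in the fixed testing sequence, and the statin limits apply to one arm only. An influence on LDL values cannot be ruled out in principle, and none can be calculated from the documents. What can be said is that no analysis specification, power or alpha depends on the correction.
- **An interim limit of 1 mg/day has a cost.** If 2 mg/day is the intended maximum, some subjects could be held to a lower dose for a time, although section 3.6.1.2 asks that lipid-lowering goals be maintained as clinically indicated. This stands as a small, temporary downside.

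**Conclusion.** The inconsistency is real. Table 2 gives pitavastatin two maxima, 2 and 1 mg/day, and section 3.6.1.2 makes the table operative for every roxadustat subject on a statin. The defect affects one of seven statins, in one arm, for doses above 1 and up to 2 mg/day.

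It is minor. The documents do not show which row is right, how many subjects take pitavastatin, or that 2 mg/day is unsafe. They also do not say whether the 2- to 3-fold rise in exposure applies to pitavastatin specifically. The conclusion rests on direct reading and assumes only that the table is reproduced faithfully.

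**What to change.** The sponsor should confirm the intended pitavastatin maximum, keep one pitavastatin row, and delete or correct the other. That includes checking whether the other row was meant for another statin. If both values were intended for different settings, each row needs a label saying so.

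Until the table is corrected, a short clarification should ask sites to use no more than 1 mg/day of pitavastatin in roxadustat subjects. Prompt confirmation by the sponsor would keep the effect of this on subjects taking more than 1 and up to 2 mg/day brief.

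The cost is one note to sites and one corrected row at the next amendment. Design, data collection, analysis and sample size stay as they are.
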